#### **9.6.6            Electrocardiogram**

The electrocardiogram (ECG) measurements from this clinical study were performed as per standard of care for routine safety monitoring, rather than for purposes of

assessment of potential QT interval corrected (QTc) effect. Because these evaluations may not necessarily be performed under the rigorous conditions expected to lead to meaningful evaluation of QTc data; neither summaries nor statistical analyses will be provided for QTc data, and these data would not be expected to be useful for meta-analysis with data from other studies.

Shift in pre- and post-baseline ECG diagnosis will be summarized.

#### **9.6.8            Exposure to Investigational Product**

**Number of IP doses received and duration of exposure to IP will be summarized.**

Subject listings of manufacturing lot numbers and a separate listing of unique manufacturing lot numbers used in this study will be provided.

#### **9.6.9            Exposure to Concomitant Medication**

All medication will be coded using the World Health Organization Drug (WHO DRUG) dictionary and a subject listing will be provided.

### **9.7                Other Analyses**

#### **9.7.1            Analyses of Pharmacokinetic or Pharmacokinetic/Pharmacodynamic Endpoints**

Serum AMG 334 concentrations will be determined using a validated assay. Individual serum concentration-time plots for AMG 334 will be presented for each subject as well as mean concentration-time plots for each dose. PK parameters will be estimated using either compartmental (eg, PK modeling) or non-compartmental methods. Actual dosing and sampling times will be used for calculation of PK parameters. Summary statistics will be generated for each PK parameter (eg, time to maximum concentration [ $t_{max}$ ],

maximum observed concentration [ $C_{max}$ ], trough concentration [ $C_{trough}$ ], and area under the concentration time curve [AUC] from 0 to 28 days [AUC0-28day]).

Clearance (CL) and central volume of distribution (Vc) on body weight basis may be summarized.

Summary statistics will be generated for each PK parameter for each treatment group. All PK-related tables, figures, listings and other deliverables will be generated by CPMS.

#### 9.7.2 Analyses of Clinical Outcome Assessments

#### 9.7.3 Neurological Assessment

Neurological assessment will be completed as per standard of care and subject incidence of abnormalities will be summarized.

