#### **4.1 Inclusion Criteria**

101. Subject's legally acceptable representative has provided informed consent and the subject has provided written assent based on local regulations and/or guidelines prior to any study-specific activities/procedures being initiated.
102. Male and female children and adolescents 6 and < 18 years of age at time of consent
103. Body weight  $\geq$  18 kg upon entry into screening
104. History of migraines, with or without aura, according to the ICHD-III for at least 12 months prior to the study screening
105. Frequency of  $\geq$  4 migraine days per month in each of the 3 months prior to the study screening period
106. Physical and neurological examinations, clinical laboratory values, and 12-lead ECGs are clinically acceptable to the investigator and Amgen medical monitor at screening

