## 2. Objectives, Endpoints and Hypotheses

### 2.1 Objectives and Endpoints

Objectives	Endpoints
Primary	

To evaluate the safety, tolerability, and pharmacokinetic (PK) profile of multiple subcutaneous (SC) doses of AMG 334 in children and adolescent subjects with migraine, respectively

	

Serum PK parameters of AMG 334 (eg, time to maximum concentration [<math>t_{max}</math>], maximum observed concentration [<math>C_{max}</math>], trough concentration [<math>C_{trough}</math>], and area under the concentration time curve [AUC] from 0 to 28 days [<math>AUC_{0-28day}</math>])

Subject incidence of treatment-emergent adverse events (AEs)

Changes in vital signs, 12-lead electrocardiograms (ECGs), clinical laboratory safety tests, and neurological assessments

Key Secondary	

Not applicable

	

Not applicable

Secondary	

Not applicable

	

Not applicable

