**5.3 Study Points of Reference**

**Baseline**

Unless otherwise stated, baseline will be defined as the last assessment taken prior to the first AMG 334 administration (ie, Day 1 pre-dose or Screening if Day 1 pre-dose is not available) of the ITP. For subjects continuing treatment in an OEP after completion of the ITP, their baseline will be the same as the ITP.

For ECG and Neurological Evaluation, the entire set of data from the Day 1 visit will be used as baseline. If the data is missing on Day 1, the entire set of data from the Screening visit will be used as baseline.

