#### **5.4 Study Time Interval**

##### **5.4.1 Study Periods**

The following data will be categorized into treatment periods, if applicable. Any data occurred after EOS date will not be included in the analysis [REDACTED]

Study Phase	Start Time Point	End Time Point
Initial Treatment Phase	Study Day 1	
For Treatment-emergent Adverse Event:
 

• Min (First OEP Dose Date – 1, EOS date) for subjects who received OEP dose;

• EOS Date, for subjects who did not receive any OEP dose

 
For lab, ECG, [REDACTED], Neurological Evaluation and Vital Signs:
 

• Min (First OEP Dose Date, EOS date) for subjects who received OEP dose;

• EOS Date, for subjects who did not receive any OEP dose

 
[REDACTED]

Study Phase	Start Time Point	End Time Point
Optional Extension Phase	For Treatment-emergent Adverse Event: • First OEP Dose Date For [REDACTED] lab, ECG, [REDACTED] Neurological Evaluation and Vital Signs: • First OEP Dose Date + 1	For Treatment-emergent Adverse Event, lab, ECG, [REDACTED] Neurological Evaluation and Vital Signs: • EOS Date
Entire Study	Study day 1	EOS

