### Subject Incidence

The subject incidence for a given event in a given period is defined as the number of subjects with at least one reported occurrence of the event divided by the number of subjects who enter that period (ie, number of at-risk subjects). For subjects with multiple occurrences of the same event in a given period, the event will only be counted once per subject in that period.

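### SAP 9.7.3 does not tie the incidence of neurological abnormalities to the baseline in SAP 5.3, so a pre-existing abnormality can be counted as an on-treatment finding and the change endpoint has no specified analysis

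*SAP*

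**What the plan says.** SAP 2.1 gives the safety part of the primary endpoint as "Changes in vital signs, 12-lead electrocardiograms (ECGs), clinical laboratory safety tests, and neurological assessments", and protocol 10.1.1 has the same item. The neurological method is one sentence in SAP 9.7.3: "Neurological assessment will be completed as per standard of care and subject incidence of abnormalities will be summarized". Protocol 10.4.2.3.4 adds only that each subject's data will be reviewed.

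Four other provisions bear on how that sentence would be carried out:

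- SAP 5.6 defines subject incidence as "the number of subjects with at least one reported occurrence of the event divided by the number of subjects who enter that period", and treats everyone who enters the period as at risk.
- SAP 5.3 sets a baseline: "For ECG and Neurological Evaluation, the entire set of data from the Day 1 visit will be used as baseline", with the Screening visit as the fallback.
- SAP 5.4.1 starts the initial treatment phase on Study Day 1. The neurological data fall under its rule headed "For lab, ECG, [REDACTED], Neurological Evaluation and Vital Signs".
- Inclusion criterion 106 in protocol 4.1 requires: "Physical and neurological examinations, clinical laboratory values, and 12-lead ECGs are clinically acceptable to the investigator and Amgen medical monitor at screening".

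**The concern.** The endpoint is a change, whereas the planned summary is a count of abnormal findings with no baseline, post-baseline or new-onset qualifier. Carried out as written, it gives a mixture of prevalence and onset.

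All subjects receive AMG 334, so there is no untreated arm against which to set pre-existing findings. Some of the dose arms are very small. A long-standing abnormality in one child could look like a sizeable neurological signal at that dose. The same summary can also hide a deterioration: a subject already abnormal at baseline counts once whether or not the finding gets worse.

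**Working it through.** The plan states no figure that depends on this point, so there is none to reproduce. The check is a reading of the provisions together, followed by simple arithmetic on size.

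**Step 1: how the components of the same endpoint are analysed**

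| Component | SAP section | Reference to baseline |
|---|---|---|
| Laboratory tests | 9.6.3 | Toxicity-grade shift tables and change from baseline by visit |
| Vital signs | 9.6.4 | Change from baseline |
| ECG | 9.6.6 | "Shift in pre- and post-baseline ECG diagnosis will be summarized" |
| Neurological | 9.7.3 | None stated |

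Only the neurological component lacks a comparison with baseline, although SAP 5.3 gives it the same baseline rule as ECG.

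**Step 2: can a pre-existing abnormality be counted?**

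- Entry: criterion 106 asks for a clinically acceptable examination, so a stable abnormality does not bar enrolment.
- Numerator: SAP 5.6 needs one occurrence in the period and has no exclusion for presence at baseline. An abnormality that persists to a later visit qualifies.
- Day 1: SAP 5.3 makes the whole Day 1 visit baseline, while SAP 5.4.1 places Study Day 1, which is a day and not a time, in the initial treatment phase. Protocol 7.2.16 lists the neurological examination as pre-dose. The same examination is thus both baseline and, by date, inside the counting period. For neurological data the extension phase starts the day after its first dose; there is no matching adjustment at Study Day 1.

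No provision says that such findings are to be counted, and none says that they are to be left out.

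**Step 3: arm sizes**

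Inputs are from SAP 3.1: at least 52 enrolled; Cohort 1 up to about 22; Cohort 2 from 35 to about 38; allocation 1:2 (35 mg : 70 mg) and 1:4 (70 mg : 140 mg). Taking the approximate limits at face value, the smallest Cohort 1 consistent with the total is 52 − 38 = 14. One carried-over subject adds 100/n points.

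| Arm | n, low to high | Points per subject |
|---|---|---|
| Cohort 1, 35 mg | 14/3 = 4.7 to 22/3 = 7.3 | 21 to 14 |
| Cohort 1, 70 mg | 28/3 = 9.3 to 44/3 = 14.7 | 11 to 7 |
| Cohort 2, 70 mg | 35/5 = 7 to 38/5 = 7.6 | 14 to 13 |
| Cohort 2, 140 mg | 28 to 30.4 | 3.6 to 3.3 |

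Over all 52 subjects, it adds 100/52 = 1.9 points.

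**Step 4: raw incidence against new onset**

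Let b be the proportion abnormal at baseline and r the new-onset rate among those normal at baseline. Both are assumptions, and baseline abnormalities are taken to persist. Raw incidence = b + (1 − b)r.

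| b | Raw, r = 0 | Raw, r = 2% | Chance of at least one among 52, 1 − (1 − b)^52 |
|---|---|---|---|
| 2% | 2% | 0.02 + 0.98 × 0.02 = 4.0% | 65% |
| 5% | 5% | 0.05 + 0.95 × 0.02 = 6.9% | 93% |
| 10% | 10% | 0.10 + 0.90 × 0.02 = 11.8% | over 99% |

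A baseline-referenced incidence would be 0% in the r = 0 column and 2% in the r = 2% column.

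**The case against.** The strongest reply is that SAP 5.3 has a baseline rule written for this very assessment, which would serve little purpose unless results were compared with it. Starting the phase on Day 1 also applies to laboratory, ECG and vital-sign data, so it does not by itself turn pre-dose results into on-treatment ones. This stands in part. A reader might infer from SAP 9.7.3 that pre-existing abnormalities will be counted as on-treatment; the documents do not support that, because they are silent and SAP 5.3 suggests that a comparison may be intended. But SAP 9.7.3 never uses that baseline. For the other components the Day 1 overlap is harmless because their methods state a change or a shift.

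A second reply is that the information comes through elsewhere. SAP Table 9-1 promises summary statistics for the endpoint. Protocol 9.1.1 makes worsening of a pre-existing condition an adverse event, and SAP 5.1 limits treatment-emergent events to those starting on or after the first dose. This softens the consequence. It does not fill the gap: Table 9-1 is generic, and adverse events capture only what the investigator reports as such, whereas neurological change is a separate part of the endpoint.

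Two further inferences should be resisted. The Cohort 1 minimum of 12 would give 4 subjects on 35 mg and 25 points per subject, but the cohort minima sum to 12 + 35 = 47, short of the required 52. And a persisting finding that appears in both the initial phase and the extension is not an error in itself: SAP 5.6 counts once per subject per period, and SAP 7.3 reports the extension separately on purpose.

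**Conclusion.** The point holds as a gap in specification with a practical consequence. A component of the primary endpoint defined as change has no stated analysis of change, and the stated summary allows pre-existing abnormalities to be reported as on-treatment findings. It is not shown that they will be.

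The per-arm sizes in the working rest on the enrolment limits and allocation ratios being met, and on one affected subject in the arm. They show how sensitive the small arms are, not how often this will happen, because the documents give no rate of neurological abnormality at entry. Carry-over pushes the reported incidence upwards, although unrecorded worsening can be masked. There is no formal hypothesis test and no stopping rule, so power, error rates and trial conduct are untouched. The matter is the interpretability of one safety table.

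**What to change.** In SAP 9.7.3:

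- Replace the raw incidence with a shift table, by body weight cohort and dose: the SAP 5.3 baseline (normal or abnormal) against any post-baseline abnormality, in line with the ECG approach.
- Report the incidence of new abnormalities, meaning those not present at baseline, and state the denominator.
- Use all post-baseline visits. The criterion should be post-baseline and not post-dose, because the examinations at Days 29 and 57 are done before that day's dose and would otherwise be lost.
- State that data serving as baseline under SAP 5.3 are not counted as initial-treatment-phase findings. This settles the overlap with SAP 5.4.1.
- Keep the raw findings as a listing, and describe any worsening of a pre-existing abnormality there. Protocol 7.2.6 specifies no grading scale, so worsening cannot be tabulated by grade.

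The cost is SAP wording and one table layout. Baseline and later neurological examinations are already scheduled, so the shift table and the new-abnormality incidence need no further examinations.

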### 10. Changes From Protocol-specified Analyses

As a change from protocol-specified analysis per protocol amendment 4 dated 20 March 2020, an unplanned interim analysis was conducted in May 2021, when at least 8 children (aged 6 to < 12 years) had completed study Week 12 assessments, to facilitate engagement with health authorities regarding modifications to the AMG 334 Pediatric Investigational Plan (PIP) and commencement of enrollment of children in AMG 334 Pediatric Phase 3 studies. An as-is database snapshot occurred and included all data up to and including corresponding data cutoff date. Safety analyses including AEs, vital sign, laboratory, ECG, [REDACTED] was summarized by GBS group. PK data was analyzed by CPMS group based on all available PK data including all adolescent and children subjects from both Cohort 1 (< 40 kg) and Cohort 2 ( $\geq$  40 kg).

The unplanned interim analysis fulfilled the requirement of second interim analysis (as described in [Section 7.1](#)), as reflected in Protocol Amendment 5 dated 03 November 2021. All TFLs generated during the unplanned interim analysis will be considered as second interim analysis outputs for the purpose of study documentation.

There is a change in timing of the primary analysis (as described in [Section 7.2](#)) compared to the Protocol Amendment 5 dated 03 November 2021.

**12. Prioritization of Analyses**

Prioritization of analyses has not been identified at this time.

**13. Data Not Covered by This Plan**

There are no plans to specifically analyze or summarize the following data:

- ECG QTc data
- Data for biomarker development
- Pharmacogenetic data

**14. Appendices**

**Appendix A. Reference Values/Toxicity Grades**

Adverse event severity and laboratory toxicity are graded based on National Cancer Institute (NCI) Common Toxicity Criteria version 4.03 or higher, which is available at the following: [https://evs.nci.nih.gov/ftp1/CTCAE/CTCAE\\_4.03/CTCAE\\_4.03\\_2010-06-14\\_QuickReference\\_5x7.pdf](https://evs.nci.nih.gov/ftp1/CTCAE/CTCAE_4.03/CTCAE_4.03_2010-06-14_QuickReference_5x7.pdf)

**Appendix B. Clinical Outcome Assessment Forms/Instruments**
